6.6.3. Clinical Global Assessment of Discharge Readiness (CGADR)

The CGADR will be used to measure a subject's current clinical status and is the clinician's assessment of the readiness to be discharged from the study site.

The clinician will answer "Yes" or "No" to the question "Is the subject considered ready to be discharged based on their overall clinical status (e.g., sedation, blood pressure, and other adverse events)?"

On each intranasal dosing day, the CGADR will be performed at 30 mins postdose, repeated every 15 minutes if necessary until the response is 'Yes'. On all intranasal treatment session days, subjects must remain at the clinical site until study procedures have been completed and the subject is ready for discharge.

The proportion of subjects with a response of 'No' at each time point will be presented by each of the treatment phases.

6.6.4. Computerized Cognitive Battery and Hopkins Verbal Learning Test-Revised (HVLTR)

The effect of intranasal esketamine on cognition will be assessed using HVLTR.

The computerized cognitive battery provides assessment of multiple cognitive domains, including attention, visual learning and memory, and executive function. The tests use culture-neutral stimuli, enabling use in multilingual/multicultural settings. The HVLT-R is a measure of verbal learning and memory and is a 12-item word list recall test. The total number of correct responses are captured for 4 trials as well as the number of true-positive responses and false-positive errors in Trial 4 (Delayed Recall). The Total Recall will be derived as the sum of trials 1, 2 and 3. Retention % will be derived as (the number of correct responses in Trial 4) / (higher score of Trials 2 and 3) * 100. Recognition Discrimination Index will be derived as the total number of true-positives - the total number of false-positives.

See [Attachment 2](#) for details of this analysis.

6.6.5. Physician's Withdrawal Checklist, 20-item (PWC-20)

At the request of the National Agency for the Safety of Medicines and Health Products in France, a 4-week Follow-up Phase was added to assess for potential withdrawal symptoms following cessation of intranasal esketamine using PWC-20 assessment. The PWC-20 will be performed at the Early Withdrawal/ End of Study Visit and every week during the 4-week Follow-up Phase after discontinuation of intranasal esketamine treatment. In order to better assess potential withdrawal symptoms from the intranasal medication it is recommended that any ongoing oral antidepressant medication be continued for the duration of the follow-up phase unless determined as not clinically appropriate.

The PWC-20 is a 20-item simple and accurate method to assess potential development of discontinuation symptoms after stopping of study drug. The PWC-20 is a reliable and sensitive instrument for the assessment of discontinuation symptoms. Discontinuation symptoms occur early and disappear rather swiftly, depending upon speed of taper, daily medication dose, and drug elimination half-life.

The proportion of subjects with withdrawal symptoms at the end of Optimization/Maintenance Phase will be presented for the subjects in France. In addition, symptoms at follow-up will be compared to the end of therapy visit and will be summarized using the following categories: new or worsened symptoms, symptoms present and unchanged, no symptoms, and improved.

	10.2.2. Overall Baseline (i.e., Comparison Pre-Drug Exposure Within 54135419TRD3008)	9
	10.3. Outcome Measures Related to Cogstate Analysis	9
	10.4. The Reliable Change Index (RCI): Comparison of Individual Scores to Baseline	12
11.	Data Quality Assurance	12
	11.1. Test Completion Criteria	13
12.	Statistical Methodology	13
	12.1. Analysis Overview	13
	12.2. Analysis of Cogstate Computerized Battery and HVLT-R	14
	12.2.1. Primary Analyses	14
	12.2.2. Exploratory Analyses	14
13.	References	15

5. Abbreviations

Abbreviation	Description
DET	Detection Test
EW	Early Withdrawal
GML	Groton Maze Learning Test
HVLT-R	Hopkins Verbal Learning Test-Revised
IDN	Identification Test
ISD	Intra-Subject Standard Deviation
OCL	One Card Learning
ONB	One Back Test
RCI	Reliable Change Index
RT	Reaction Time
SAP	Statistical Analysis Plan
SAS	Statistical Analysis System
TLF	Tables, Listings and Figures
TRD	Treatment-Resistant Depression

6. Introduction

This Statistical Analysis Plan (SAP) contains a more technical and detailed elaboration of the principal features of the analysis described in the 54135419TRD3008 Study Protocol related to Cogstate computerized battery and the Hopkins Verbal Learning Test – Revised (HVLTR) and includes detailed procedures for executing the statistical analysis of the Cogstate battery data.

The SAP is finalized and signed prior to database lock. If needed, revisions to the approved SAP may be made prior to database lock. Revisions will be version controlled.

Any changes from the analyses planned in the SAP will be justified in the Cogstate statistical report.

Prior to database lock, a review of all tables, listings, and figures will occur. This requires the sponsor to send Cogstate SDTM FT and SUPPFT datasets for both the computerized tests as well as the Hopkins Verbal Learning Test – Revised (HVLTR), in addition to an ADSL dataset. The same datasets will be requested again immediately after database lock (for both the interim and final analyses) to perform the statistical analyses.

7. Study Objectives Related to Cogstate

The primary objective of this study is to assess the safety and tolerability of intranasal esketamine in subjects with Treatment-Resistant Depression (TRD), with special attention to potential long-term effects on cognitive function.

8. Study Design

8.1. General Description

This is a multicenter, open-label long term extension study to evaluate the safety, tolerability, and efficacy of intranasal esketamine in subjects with TRD. This study has 2 open label phases:

- *A 4-week induction phase*
- *A variable duration optimization/maintenance phase*

Induction Phase

Subjects will self-administer open-label intranasal esketamine as a flexible dose regimen twice a week for 4 weeks [as outlined in Study Protocol Section 6.1.1].

At the end of the induction phase, subjects may be eligible to proceed to the optimization/maintenance phase, according to the investigator's clinical assessment of the benefit versus risk for the subject.

If a subject withdraws from the study before the end of the induction phase for reasons other than withdrawal of consent or is not eligible to proceed to the optimization/maintenance phase, an Early Withdrawal (EW) visit will be conducted within 1 week of the last intranasal dose.

Subjects who are currently in the induction phase at the time the 54135419TRD3008 study is completed will conduct an "End of Study" visit as their final study visit within 1 week of the last intranasal dose.

Optimization/Maintenance Phase

[figure not shown]
During this phase, the dose and intranasal treatment session frequency can be adjusted based on the criteria outlined in [Study Protocol Section 6.1.2].

If a subject withdraws from the study before the end of the optimization/maintenance phase for reasons other than withdrawal of consent, an EW visit will be conducted within 1 week of the last intranasal dose.

Subjects who are currently in the optimization/maintenance phase at the time the 54135419TRD3008 study is completed will conduct an “End of Study” visit as their final study visit within 1 week of the last intranasal dose.

8.2. Schematic Design

Figure 1: Schematic Overview of Study 54135419TRD3008

*28mg dose only an option for subjects ≥ 65 years

8.3. Scheduled Visits

Table 1: Visit Schedule for Cogstate Computerized Cognitive Battery and HVLTR

Analysis Phase	Scheduled Day ^a	Time Interval ^a (label on output)	Time Interval ^a (Day)	Target Time Point ^a (Day)	Analysis Visit
IND	1	Baseline	≤ 1	1	Yes
	28	Day 28 (IND)	2 to end of IND	28	Yes
	IND final visit	End Point (IND)	2 to end of IND		Yes
OP/MA i = 1, 2, 3...	15	Week 3 (OP/MA)	1-60	15	Yes
	106	Week 16 (OP/MA)	16 – 148	106	Yes
	106 + i *84	Week (16 + i *12) (OP/MA)	65 + i *84 to 148 + i *84	106 + i *84	Yes
	OP/MA final visit	End Point (OP/MA)	1 to end of OP/MA		Yes

^a For IND phase, time interval is relative to the first day of the induction phase.

For OP/MA phase, time interval is relative to the first day of the optimization/maintenance phase.

9. Analysis Set and Population

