Study Procedures												
Screening/Administrative												
Informed consent (prior to any procedure; except subjects entering phase from 54135419TRD3008 Induction Phase)	X											
Inclusion/exclusion criteria (predose; except subjects entering phase from 54135419TRD3008 Induction Phase)	X											
Study Drug												
Esketamine nasal spray treatment session ^{f),t)}	X	X ^{g)}	X	X ^{g)}		X ^{h)}						
Adjustment of intranasal treatment session frequency (if applicable) based on CGI-S				X		X	X					
Drug accountability (intranasal study medication)	X	X ⁱ⁾	X	X ⁱ⁾		X ⁱ⁾						
Efficacy Assessments (Clinician)^{j)}												
MADRS	X		X				X				X	
CGI-S	X	X	X	X		X					X	
Subject-Completed Assessments^{j)}												
PHQ-9	X		X						X		X	
SDS	X		X						X		X	
EQ-5D-5L	X		X						X		X	
TSQM-9	X								X		X	
QLDS ^{r)}	X		X						X		X	
Patient Stated-choice Preference Survey ^{k)}				X ^{l)}							X ^{l)}	
Safety Assessments (Clinician)												
Physical examination, weight	X								X ^{l)}		X	
Vital signs (predose): blood pressure, pulse, respiratory rate, and temperature	X	X ^{l)}	X	X ^{l)}	X ^{l)}							
Vital signs (postdose): blood pressure, pulse, and respiratory rate only ^{m)}	X	X ^{l)}	X	X ^{l)}	X ^{l)}							
12-lead electrocardiogram ⁿ⁾	X						X				X	
CSSRS ^{o)}	X	X ^{l)}	X	X ^{l)}		X					X	
MOAA/S ^{o)}	X	X ^{l)}	X	X ^{l)}								

Phase	Optimization/Maintenance Phase											Early Withdrawal/ End of Study ^{e)}
	Visit Number	2.1 ^{b),c)}	2.2	2.3	2.4	2.5 to 2.X						
	Study procedure frequency (following Week 4) through end of phase											
Week	1	2	3	4	5, 6, 7, 8, etc	6, 8, 10, etc	8, 12, 16, etc	12, 20, 28, etc	16, 28, 40 etc	28, 52, 76, etc		
Day	1	8	15	22	Every week	Every 2 Weeks	Every 4 Weeks	Every 8 Weeks	Every 12 Weeks	Every 24 Weeks		
Clinic (C) or Remote (R) Visit ^{a)}	C	C or R	C	C or R	C ^{g)}	C or R	C	C	C	C	C	
Pulse oximetry ^{d)}	X	X ^{h)}	X	X ^{h)}								
CGADR ^{p)}	X	X ^{h)}	X	X ^{h)}	X ^{h)}							
Cognitive Testing												
Computerized cognitive battery and HVLTR-R ^{j)}			X						X		X	
Clinical Laboratory Tests												
HbA1c ^{q)}	X									X		
Hematology and chemistry ^{j)}	X								X		X	
Urinalysis ^{j)}	X								X		X	
Urine drug screen ^{j)}	X								X			
Alcohol breath test ^{j)}	X											
Urine pregnancy test ^{j)} (only for females of child bearing potential)	X						X				X	
Medical Resource Utilization												
HRUQ ^{l)}	X			X								
Ongoing Subject Review												

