2.3. Visit Windows

As subjects do not always adhere to the protocol visit schedule, the following rules are applied to assign actual visits to protocol visits. Listed below are the visit windows and the target days for each visit. The reference day is Study Day 1 (which is the first day that any study drug was taken in the induction phase for subjects who enter the study at the induction phase, and the first day any study drug was taken in the optimization/maintenance phase for responders from induction phase and subjects directly entering the optimization/maintenance phase of this study).

If a subject has 2 or more scheduled or unscheduled visits in one visit window, the visit closest to the target day will be used as the protocol visit for that visit window. If 2 actual visits are equidistant from the target day within a visit window, the later visit is used. If a visit window has no scheduled visits but does have unscheduled visits, then the unscheduled visit closest to the scheduled visit will be used.

All assignments will be made in chronological order. Once a visit is assigned to a visit window, it will no longer be used for a later time point except for the end point.

Listed below are the visit windows and the target days (if applicable) for each visit defined in the protocol for all phases (Table 1).

Table 1: Analysis Visits

Parameter	Analysis Phase	Scheduled Day ^a	Time Interval (label on output)	Time Interval ^a (Day)	Target Time Point ^a (Day)
Montgomery-Asberg Depression Rating Scale (MADRS)	IND	1	Baseline	≤ 1	1
		8	Day 8 (IND)	2 - 11	8
		15	Day 15 (IND)	12 - 18	15
		22	Day 22 (IND)	19 - 24	22
		28	Day 28 (IND)	25 to end of IND	28
		IND final visit	End Point (IND)	2 to end of IND	
	OP/MA i=1,2,3,...	1	Baseline (OP/MA)	≤ 1	1
		15	Week 3 (OP/MA)	2 - 32	15
		50	Week 8 (OP/MA)	33 - 64	50
		50 + i*28	Week (8 + i*4) (OP/MA)	37 + i*28 to 64 + i*28	50 + i*28
OP/MA final visit		End Point (OP/MA)	2 to end of OP/MA		
CGI-S	IND	1	Baseline	≤ 1	1
		4	Day 4 (IND)	2 - 6	4
		8	Day 8 (IND)	7 - 9	8
		11	Day 11 (IND)	10 - 13	11
		15	Day 15 (IND)	14 - 18	15

Table 1: Analysis Visits

Parameter	Analysis Phase	Scheduled Day ^a	Time Interval (label on output)	Time Interval ^a (Day)	Target Time Point ^a (Day)
		22	Day 22 (IND)	19 - 24	22
		28	Day 28 (IND)	25 to end of IND	28
		IND final visit	End Point (IND)	2 to end of IND	
	OP/MA i=1,2,3,...	1	Baseline (OP/MA)	≤ 1	1
		8	Week 2 (OP/MA)	2 - 11	8
		15	Week 3 (OP/MA)	12 - 18	15
		22	Week 4 (OP/MA)	19 - 29	22

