12.2. Analysis of Cogstate Computerized Battery and HVLTR

12.2.1. Primary Analyses

Note: For both comparisons of interest (i.e., against First Baseline and Study Baseline), all analyses summarized in this section will be conducted for all subjects as well as by age group (i.e., <65 years old and ≥ 65 years old).

Score and change from baseline scores for the Cogstate Battery and HVLTR tests will be tabulated descriptively (n, mean, median, SD, min, max) by timepoint across the induction phase and optimization/maintenance phases. Intra-subject standard deviation, which is the standard deviation across all log₁₀ transformed reaction times for correct responses made within a given test administration, will also be summarized across timepoints for the Detection and Identification tests.

Line plots will be generated for the Cogstate Battery and HVLTR tests, reflecting the Mean (+/-SE) of the scores at each timepoint for each dose level.

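### The Week 16 cognition window in SAP Attachment 2 starts on Day 16 and overlaps the Week 3 window by 45 days, so a second early test can be tabulated as Week 16

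*SAP*

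**What the plan says.** Attachment 2 is the only place where the SAP gives analysis windows for cognition. SAP section 2.3 introduces its own Table 1 with "Listed below are the visit windows and the target days (if applicable) for each visit defined in the protocol for all phases", but that table has no cognition rows. SAP section 6.6.4 sends the reader to Attachment 2 "for details of this analysis".

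The relevant rows of Attachment 2, section 8.3, Table 1 ("Visit Schedule for Cogstate Computerized Cognitive Battery and HVLTR"), counted from the first day of the optimization/maintenance (OP/MA) phase, are:

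| Visit | Window (days) | Target day |
|---|---|---|
| Week 3 | 1 to 60 | 15 |
| Week 16 | 16 to 148 | 106 |
| Week 16 + 12i, i = 1, 2, ... | 65 + 84i to 148 + 84i | 106 + 84i |
| End Point | 1 to end of phase | none |

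Attachment 2 has no rule for choosing among tests that compete for a window. SAP section 2.3 has three that matter here. With several visits in a window, "the visit closest to the target day will be used as the protocol visit for that visit window". Assignment is chronological. Once a visit has been assigned, "it will no longer be used for a later time point except for the end point".

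In the Protocol's Time and Events Schedule for this phase, the row "Computerized cognitive battery and HVLTR-R" is marked at Visit 2.3 (Day 15), every 12 weeks from Week 16, and at Early Withdrawal/End of Study. Under Attachment 2, section 8.1, "an EW visit will be conducted within 1 week of the last intranasal dose". Attachment 2, section 12.2.1, then tabulates scores and changes "by timepoint across the induction phase and optimization/maintenance phases".

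**The concern.** A set of analysis windows should give each day at most one scheduled visit. Here, any test on Days 16 to 60 qualifies for both Week 3 and Week 16. Early withdrawal is the ordinary way for a subject to have a second cognition test in that span, so the tests at risk of a wrong label come mainly from people leaving the study.

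Potential long-term effects on cognition come first in the list under the primary objective (Protocol 2.1.1, SAP 1.1). The Week 16 label feeds the descriptive tables against both baselines, overall and by age group, and the line plots by dose level. It also feeds the exploratory reliable-change plots in subjects aged 65 or older. Attachment 2, section 9.4, rules out imputation for dropouts and omitted visits. The printed window can nevertheless fill an empty Week 16 cell with a test taken in the Week 3 period.

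**Working it through.** **Overlap as printed.** Week 3 covers Days 1 to 60 and Week 16 covers Days 16 to 148. The common days are 16 to 60: 60 − 16 + 1 = 45 days.

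**What the neighbouring limits imply.** The SAP states no midpoint rule, but the other limits fit one.

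- Week 3 and Week 16 targets: (15 + 106)/2 = 60.5. The printed Week 3 end is Day 60, so the next window would start on Day 61.
- Week 16 and Week 28 targets: (106 + 190)/2 = 148. The printed Week 16 end is Day 148.
- Week 28 start: 65 + 84 = 149, the day after 148.

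Only the Week 16 start departs from the pattern. With Days 61 to 148 there is no overlap with Week 3 and no gap. That 16 is a reversal of the digits of 61 is a natural inference, but the overlap does not depend on it.

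**Distance to target.** Every overlap day is nearer Day 15 than Day 106. Day 60, the closest call, is 45 days from Day 15 and 46 from Day 106. Day 61 is 46 and 45.

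| Window | Length (days) | Days before target | Days after target |
|---|---|---|---|
| Week 16 as printed, 16 to 148 | 133 | 106 − 16 = 90 | 148 − 106 = 42 |
| Week 16 from Day 61 | 88 | 106 − 61 = 45 | 42 |
| Week 28, 149 to 232 | 84 | 190 − 149 = 41 | 232 − 190 = 42 |

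A test that enters Week 16 through the overlap is therefore 46 to 90 days before target.

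**Applying section 2.3** (chronological, closest to target, later if tied, no re-use):

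| Test days | Printed window | Window from Day 61 |
|---|---|---|
| 15, 36 | Week 3 = 15, Week 16 = 36 | Week 3 = 15 |
| 15, 60 | Week 3 = 15, Week 16 = 60 | Week 3 = 15 |
| 15, 36, 106 | Week 3 = 15, Week 16 = 106 | same |
| 15, 60, 61 | Week 3 = 15, Week 16 = 61 | same |
| 40 only | Week 3 = 40 | same |
| 5, 20 | Week 3 = 20 | same |

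Any test on Days 61 to 148 is at most 45 days from target, and any test on Days 16 to 60 is at least 46 days away, so a test on Days 61 to 148 always wins. The wrong label needs a Week 3 test, another test by Day 60, and none on Days 61 to 148.

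There are 1,665 two-test patterns with the second test on Days 16 to 60 and nothing later. In 1,560 of them the second test goes to Week 16; in the other 105 it is itself the Week 3 choice. These are counts of day combinations, not a probability or a number of subjects.

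**Other windows.** Consecutive scheduled windows were compared for every assessment in SAP Table 1 and Attachment 2 Table 1, with recurring windows taken to i = 5. Of 120 pairs, 119 are contiguous. This is the only pair that overlaps. The total of 120 depends on how baseline rows and recurring windows are counted.

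**The case against.** The strongest reply is that section 2.3 can be read so that the overlap does nothing. On that reading, Days 15 and 40 are both assigned to the Week 3 window, Day 15 is the one reported, and Day 40, being already assigned, is barred from Week 16 and counts only towards End Point. This is possible but weaker. Section 2.3 assigns actual visits to protocol visits and takes the closest one as the protocol visit. Its statement that an assigned visit will no longer be used implies that the visit was used. Two defensible readings with different Week 16 tables are in any case a reason to correct the number.

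The second reply is that the harm is small. The case is narrow, there is no formal hypothesis, the summaries are descriptive, and the long-term question rests on later windows that are unaffected. All of that stands and limits the weight of the point.

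The third is that the SAP accepts similar labelling elsewhere. Week 16 for laboratory tests, weight and urinalysis runs from Day 2 to Day 148, so a Day 40 withdrawal sample is labelled Week 16 there by design. That is true, but those assessments have no earlier post-baseline OP/MA window, so no day has two labels. The fault claimed here is the overlap, not the width.

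**Conclusion.** The concern holds. The printed Week 16 window overlaps Week 3 by 45 days, and Day 61 is the only start that leaves neither overlap nor gap with the other limits as printed. As the sole window specification for cognition, this is a wrong analysis rule and should be fixed, though it does not threaten the study's conclusions.

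The tabulation of a Day 16 to 60 test as Week 16 rests on two assumptions: that section 2.3 governs Attachment 2, and that a visit is used up only when it is selected for a window. If section 2.3 does not apply, the table leaves such a test without a unique visit.

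The reach is one descriptive timepoint. Subjects with a single test on Days 1 to 60, or with any test on Days 61 to 148, are unaffected. How many subjects are involved, and in which direction the Week 16 mean might move, cannot be worked out from the documents.

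**What to change.** In Attachment 2, section 8.3, Table 1, change the Week 16 (OP/MA) window to Days 61 to 148. Add one sentence to Attachment 2 saying that the assignment rules of SAP section 2.3 apply to the cognition tests. Leave the Day 1 starts of Week 3 and End Point (OP/MA) as they are.

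The cost is one number and one sentence, with no new data. Attachment 2 allows revision before database lock. If lock has passed, the cognition report should state which window was programmed and justify any departure from the printed one.

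The correction removes only tests more than 45 days before target. Early-withdrawal tests on Days 61 to 105 can still be labelled Week 16.

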9.1. Unblinding Procedure

As this study is open-label, blinding procedures are not applicable.

9.2. Analysis Set

9.2.1. All Enrolled Analysis Set

All subjects who were eligible to enter this study and received at least one dose of intranasal esketamine.

9.3. Sample Size and Analysis Population

No formal sample size calculation was performed. The study population will include adult and elderly men and women who previously participated in studies ESKETINTRD3001, ESKETINTRD3002, ESKETINTRD3003, ESKETINTRD3004, or ESKETINTRD3005, or ESKETINTRD3006 (US sites only).

9.4. Handling of missing data

No imputations will be performed in the event of missing data due to dropouts or omitted visits. All incomplete subject profiles will be retained in the analysis. In view of issues of reliability, all analyses will be conducted with completion failures removed.

10. Analysis Endpoints, Baseline Definition, and Outcome Measures

10.1. Analysis Endpoints

The analysis endpoint for each of the tests in the Cogstate computerized cognitive battery and for the Hopkins Verbal Learning Test-Revised (HVLT-R) is change from baseline scores over time.

10.2. Baseline Definitions

10.2.1. First Baseline (i.e., Comparison to Pre-Drug Exposure)

For all subjects enrolled in 54135419TRD3008 (except for those subjects entering from ESKETINTRD3006), baseline is defined as Baseline (IND) (i.e., Study Day 1) of the first study from which they have entered. For example, if a subject participated in study TRD3005 and went to TRD3004 and then finally joined 3008, the first baseline will be the Baseline (IND) from study TRD3005.

